Plan for developing a formal study protocol [RQ-2]. The co-PIs will finalize the draft of the Manual of Operations, clinical research forms, and consent forms during the first month of the study period. Site investigators from participating centers and our Parent Partners will be invited to provide feedback in writing and/or during a teleconference, and the PIs will incorporate this feedback prior to finalizing the documents. For the parent and family well-being aim (Aim 3), our co-investigator [name] will work with our Parent Partners to refine the co-developed protocol for measuring parent and family psychosocial dimensions, including administering the validated instruments at the time of initial hospital discharge and at the 12-month, 18-month, and 24-month follow-ups.

Study Procedures (Table 1). (1) Neonatal Clinical Data. Clinical and demographic data will be collected from the hospital charts during the neonatal admission (Appendix 1). (2) Follow-up Outpatient EEG. A 1-hour EEG will be obtained at 2-4 months corrected age, and two investigators who are blinded to treatment duration and outcome will score the studies according to published criteria^{24,25} (Appendix 2). (3) Follow Up. A trained member of the study team, who is blinded to treatment duration, will contact families to administer a validated follow-up instrument to measure functional developmental outcome (The Warner Initial Developmental Evaluation of Adaptive and Functional Skills (WIDEA FS)) and follow-up questionnaires to determine the rates and types of epilepsy at 12, 18, & 24 months old(Appendices 3 & 4). (4) Parent and family well-being. Validated instruments to measure selected dimensions of well-being and open-ended free-text guestions specific to the impact of anticonvulsant treatment impact on parents and families will be administered at the time of hospital discharge and concurrent with the other assessments (Appendix 5).
Table 1: Study Procedures and Measurements.

Study Measurements	Examples			
Neonatal Clinical Data (Appendix 1)				
- Demographics	Sex, birth weight, gestational age at birth, mode of delivery, etc.			
- Seizure etiology	HIE/ischemic stroke/intracranial hemorrhage/intracranial infection/other (based on chart review and neuroimaging findings)			
- Seizure characteristics	Presence and frequency of electrographic seizures, including presence of status epilepticus			

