Preliminary data suggest adequate heterogeneity in clinical practice to examine short *versus* **prolonged phenobarbital duration within our established multi-center registry.** Unpublished data from our *Neonatal Seizure Registry* indicate heterogeneity for neonatal seizure treatment. Among 306 consecutive newborns enrolled in the *Neonatal Seizure Registry* for acute symptomatic seizures who survived to discharge, 23% had medication discontinued prior to discharge (range by site 3 to 75%), while 77% continued on anticonvulsants. In multivariate analyses, treating institution was the only independent predictor of continued medication after *discharge to home* (p<0.001); neither seizure burden nor etiology of acute symptomatic seizures predicted this treatment decision (p>0.1). Phenobarbital was the most commonly prescribed anticonvulsant (89% of those maintained on medication).

Outcome selection [RQ-6]. Our proposed outcome measures are all highly relevant to parent stakeholders. *Primary outcome.* After discussion with Parent Partners, we selected the Warner Initial Developmental Evaluation of Adaptive and Functional Skills (WIDEA FS), a simple, free, one-page assessment that will be administered by telephone at age 12, 18, and 24 months to determine functional developmental outcome (Aim 1a).²⁰ In order to administer the WIDEA FS, the examiner (who is blinded to the treatment group) asks the parent a series of questions to determine which specific developmental milestones have been gained in the following domains: Feeding, Dressing, Diaper Awareness, Mobility, Communication, and Social Cognition. The results are tabulated and scored against norms for age for children ages 0-36 months. The WIDEA FS takes about 20-30 minutes to administer, and requires minimal training for the research team. [name] (Co-

PCORI Research Plan version 2 8/1/2016

Investigator) – a neonatologist and developmental pediatrician with extensive experience establishing neurodevelopmental outcomes from clinical trials – will oversee all aspects of the developmental outcome aim. She is trained to use and teach the WIDEA FS, and will train a research coordinator from each site to perform the measure.

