according to pre-clinical studies⁴². Therefore, levetiracetam could have less impact than phenobarbital on neurodevelopmental outcomes. We will analyze the small subset of infants who are maintained on levetiracetam as a separate subgroup to obtain preliminary data regarding the impact of this medication on neurodevelopmental outcomes, epilepsy, length of stay, and parent and family well-being.

Subject recruitment. A study investigator or research coordinator will identify eligible newborns during the neonatal admission at each of the participating study sites. A study investigator will approach the parents/guardians of eligible patients and, using a consent form approved by the local Institutional Review Board, will describe the anticipated risks and benefits of the study. The consent team will include only experienced team members who are sensitive to the vulnerable nature of this population and who emphasize the voluntary nature of research. Since this study will place infants at no more than minimal risk, and could augment patient care through standard provision of the follow-up EEG, we anticipate excellent consent rates. Based on feedback from our Parent Partners, we have also attempted to minimize burden to families, and loss to follow-up, through use of a telephone-based follow-up assessment, rather than requiring in-person developmental testing.

Barriers to recruitment. Based on our extensive collective experience with long-term follow-up for neonates at risk for epilepsy – for example the PIs' NIH-supported studies (5K23HD068402, K23NS066137) and the Prevention of West Syndrome study (funded by CURE), as well as the UCSF P01NS082330-01 *Repair after Neonatal Brain Injury, which has enrolled and followed more than 750 neonates since its inception in the 1990s* – we anticipate optimal recruitment when families are approached prior to hospital discharge. Since some of the *Neonatal Seizures Registry* sites draw patients from significant geographical distances, families will be provided a stipend to off-set travel expenses associated with the follow-up EEG. The EEG will be paid for by the PCORI grant, unless the treating physician orders it on clinical grounds.

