All study participants will be followed longitudinally per local clinical guidelines through the Pediatric Neurology and/or Intensive Care Follow Up Programs. Children meeting study eligibility criteria are routinely followed through early childhood because of their risk for neurodevelopmental disability and epilepsy. A research coordinator will maintain frequent contact with the families to improve retention.

F. Research Team and Environment

Capabilities of the Research Team

Study Sites for the Neonatal Seizure Registry and for this application were chosen based on the following:

- Ability to perform continuous, video-EEG as recommended by the American Clinical Neurophysiology Society³⁷
- 2) Neurophysiologist(s) with experience interpreting neonatal and pediatric EEG
- 3) Technologists with experience in applying the neonatal EEG montage
- 4) State of the art neonatal neurology and pediatric epilepsy care

The study sites are tertiary children's hospitals located across the U.S.A. These sites provide care to a diverse range of children from all races, ethnicities, and socioeconomic strata. Therefore, we are confident that the enrolled newborns and families will be representative of the American population and that the treatment recommendations derived from the study results will be easy to implement in real-world settings.

Investigators for this study have been working together for several years, initially as part of the *NEonatal Seizure Treatment Trial* (NESTT) group (which was established using seed funding from the Child Neurology Foundation), and more recently through the *Neonatal Seizure Registry* (which was established using seed funding from the Pediatric Epilepsy Research Foundation). We have a strong track record of collaborative academic accomplishments, including management guidelines and a recent, high-impact original science paper in *Neurology*^{24,37,43}. Furthermore, we have shown that we are capable of enrolling relevant newborns, now with more than 480 consecutive neonates enrolled into the *Neonatal Seizure Registry*.

Investigators

[name], co-PI, is Clinical Associate Professor of Pediatrics and Communicable Diseases (Division of Neurology) at the University of Michigan. She completed her training in in Child Neurology and in Clinical

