APPENDIX (optional)

Appendix 1: Neonatal Seizure Registry Case Report Form

Confidential

Neonatal Seizure Registry	Neonatal Seizure Registry Page 1 of 10
Neonatal Seizure Registry	
Patient Information	
Study ID	
Institution	 01 UCSF 02 University of Michigan 03 Massachusetts General 04 Lucile Packard Children's Hospital 05 Brigham and Women's 06 Children's National Medical Center 07 Children's Hospital Boston 08 Children's Hospital of Philadelphia (Indicate one answer only. Study IDs should be written in the following 5-digit format 01001, 01002, 01003, etc. with the first two digits being the institution number.)
Sex	 ○ Female ○ Male ○ Indeterminate
Race	 American Indian / Alaska Native Asian Black / African American White Native Hawaiian / Other Pacific Islander Other More than one race Unknown / Not Reported (Indicate one answer only. See MOP for race definitions.)
Ethnicity	 Hispanic or Latino NOT Hispanic or Latino Unknown / Not reported (Indicate one answer only. See MOP for race definitions.)
Age in hours at admission (e.g. for 1hr30min, indicate 1.5)	(Use provided excel spreadsheet calculator to determine age. Age in hours should be recorded to one decimal point.)
Patient enrolled in a concurrent study?	 No Yes - observational study Yes - interventional study Unknown (Check all that apply)
Name of observational or interventional study	

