- The family will be given a reminder telephone call several days before the 2-4 month visit.
- Contact information will be verified and updated when the family comes to the 2-4 month EEG.
- If a family misses the 2-4 month EEG, then they will be contacted via telephone call within 3 days of the missed appointment. If there is no response, then an email will be sent after 5-7 days and/or a telephone call will be placed to the alternate phone number. The EEG will be rescheduled if at all possible.
- When the infant reaches 11 months, a letter will be mailed and/or emailed to the family, to remind them of the 12month telephone assessment. Families will be asked to contact the study coordinator to arrange a mutually convenient time for the 12-month telephone interview. If the family does not reply, the study coordinator will contact them via telephone and/or email to confirm an appointment for the follow-up assessment.
- In the event that an enrolled infant dies, the site's electronic medical record will be updated per local protocol. Many of the sites utilize an electronic medical record that automatically notifies a study team of a participant's death. The site study coordinators will verify that the patient is listed as living prior to extending an invitation for follow-up. If the patient is listed as deceased, the family will not be contacted.
- If a family withdraws from the study, the coordinators will attempt to document the reason for withdrawal so that issues can be identified and addressed.

Data Collection to Address Confounding: We will prospectively collect data for potential confounders to allow for the planned propensity scoring analysis, including:

- Term versus preterm at birth
- Confirmation of electrographic seizures versus diagnosis on clinical grounds alone
- Severity of seizures
- Etiology of seizures
- Number of seizure medications during the inpatient hospitalization
- Highest recorded phenobarbital level
- Abnormal neurological examination (consciousness, tone, or reflexes) at the time of discharge
- NICU length of stay
- Institution

Robust Analysis of Confounding Factors [DR-3]: Our plans to address analysis of confounding factors are addressed in the application's data analysis plan sections (see pages 9-12).

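### Blinding of the WIDEA interviewer is asserted but not secured: a coordinator at the infant's own site gives the measure, and no separation of roles is described

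*Combined protocol and SAP*

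**What the plan says.** Two places claim blinding. Study Procedures, item 3, says: "A trained member of the study team, who is blinded to treatment duration, will contact families". The primary-outcome paragraph of Outcome selection likewise calls the WIDEA examiner blinded to treatment group. That paragraph then assigns the work: the co-investigator overseeing the developmental aim "will train a research coordinator from each site to perform the measure".

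Other sections give coordinators further duties:

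- Subject recruitment: "A study investigator or research coordinator will identify eligible newborns during the neonatal admission at each of the participating study sites".
- End of Patient Population, on retention: "A research coordinator will maintain frequent contact with the families to improve retention".
- Appendix 6, loss to follow-up, when a family does not reply to the 12-month reminder: "the study coordinator will contact them via telephone and/or email to confirm an appointment for the follow-up assessment".
- Appendix 6, same list: "The site study coordinators will verify that the patient is listed as living prior to extending an invitation for follow-up".

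The registry case report form (Appendix 1) builds the study ID "with the first two digits being the institution number". Study Procedures has the same caller give the epilepsy questionnaire (Appendix 4) at 12, 18 and 24 months.

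**The concern.** Each WIDEA item is scored from 1 to 4 in conversation with a parent, and adjacent categories differ only by how often the child does something. The interviewer therefore has some discretion. If the interviewer knows the treatment group, scoring can drift with it.

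This is the primary outcome of a non-inferiority comparison whose stated hypothesis is no difference. Drift that favours the short group, or hides a true deficit in it, raises the chance of wrongly declaring non-inferiority. The plan relies on interviewer blinding against this, so it should show how that blinding is kept.

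**Working it through.** **1. Roles side by side.** The WIDEA goes to a coordinator at each site. Coordinators may screen infants in hospital (the text says investigator or coordinator), keep contact with families, arrange the calls and check vital status. Appendix 6, on protocol modifications, speaks of each site's coordinator in the singular. That suggests one per site but does not prove it. The text supplied names no second, separated coordinator, no limit on what the interviewer may see, and no test of blinding.

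**2. The epilepsy questionnaire.** Appendix 4 question 2 asks whether the newborn seizure medicine was stopped. One answer is that it stopped before leaving hospital, which is how the plan defines short duration. A caller who asks this at 12 or 18 months and calls again at 24 months has been told the group before the primary assessment. Giving the WIDEA first within each call protects only the first call.

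**3. The site code.** In the registry 23% had medication stopped before discharge, ranging from 3% to 75% by site. Guessing prolonged for every infant is right 77% of the time. Knowing the site, the best guess is right 97% of the time at the 3% site and 75% at the 75% site. A caller at the infant's own site already knows the site, so the prefix adds almost nothing. It would matter for a caller from elsewhere.

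**4. Sensitivity of the primary test.** The plan's own figure first. Inputs from Sample Size Calculations, Aim 1a: SD 16.5, limit 7, one-sided 5%, power 80%. With the registry split 23:77,

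N = (1.645 + 0.842)² × 16.5² / (7² × 0.23 × 0.77) = 194,

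or 195 after rounding each group up (150 + 45). The plan states 192, so it is reproduced to within 2%.

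Next, let scoring differ between groups by *b* points, with N = 192 (44.16 short, 147.84 prolonged) and SE = SD × √(1/44.16 + 1/147.84).

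- 12 months: SE = 16.5 × 0.1715 = 2.83.
- 24 months: the plan gives no SD. Scaling with the limit gives 16.5 × 4.25/7 = 10.0, so SE = 1.72. This is an assumption.

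Shift favouring short: error = Φ(b/SE − 1.645). Shift against short: power = Φ((limit − b)/SE − 1.645).

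| Shift *b* (points) | Error, limit 7 | Error, limit 4.25 | Power if shift is against short, limit 7 | Same, limit 4.25 |
|---|---|---|---|---|
| 0 | 5.0% | 5.0% | 79.6% | 79.6% |
| 0.5 | 7.1% | 8.8% | 74.3% | 70.5% |
| 1 | 9.8% | 14.4% | 68.3% | 59.8% |
| 2 | 17.4% | 31.5% | 54.9% | 36.9% |
| 3 | 27.9% | 54.0% | 40.9% | 18.0% |

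With the planned 90:210 split, a 1-point shift gives errors of 10.4% and 15.6%. The limits are read as points. The plan writes both 7% and −7, and the reproduction above works in points. The range of *b* is chosen for illustration; nothing in the documents estimates it.

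**The case against.** The strongest reply is that a shared job title is not a shared person. Each site could name a coordinator who does only the blinded calls, and every sentence quoted would still be true. The Manual of Operations, where such detail would sit, is not among the documents, and some passages were removed. This stands, and it limits the conclusion to blinding that is not secured.

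Three stronger readings are tempting and also fail:

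- A reader might infer that the coordinator collected the discharge medication and so knows the group for nearly every infant. No section says so. Appendix 6 describes coordinator training and data checks; recruitment text gives data collection to study personnel, and chart review for missing data falls to site investigators.
- A reader might infer that the EEG form carries the registry ID and so shows readers the site. The EEG form has only a blank subject number; nothing equates the two.
- A reader might expect a shift of several points, close to the whole 4.25 limit. No passage supports a size or a direction.

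It is also fair that a scoring habit common to a whole site is an institution effect, and institution is in the propensity model. Only scoring that differs by group among comparable infants does harm. Finally, the parent knows the treatment, so a perfectly blinded interviewer would still leave a parent-reported outcome from an unblinded respondent. That is a reason to describe the outcome accurately; the interviewer's part is the one the plan claims to control.

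**Conclusion.** The concern holds in limited form. The plan claims a blinded WIDEA interviewer, places that interviewer at the infant's own site in a role with other contact with the infant and family, and describes no safeguard. Appendix 4 question 2 adds a direct route by which a repeat caller learns the group before 24 months.

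It would go too far to say that the primary outcome is in fact assessed unblinded: the documents show overlapping roles and an unprotected call script, not what any interviewer knows. The size of any bias is unknown. The calculation shows only that the test is sensitive, with an error of 14.4% instead of 5% for a 1-point shift favouring the short group at 24 months. That figure assumes 192 infants split 23:77, a 24-month SD near 10 and a limit in points. This is a worthwhile, low-cost improvement, not a fatal flaw.

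**What to change.** 1. Have each WIDEA given by an already-trained coordinator from a site other than the enrolling one, with no part in that infant's screening, medication data or retention contact. Failing that, state who interviews and what they may not see.
2. Give the WIDEA before the epilepsy questionnaire. Take question 2 from the chart, or have someone else ask it, so that a repeat caller is not told the group. Without this step, exchanging coordinators does not protect the 24-month assessment.
3. Put a follow-up ID without the institution prefix on the call sheet.
4. Record the interviewer's guess of treatment group straight after each WIDEA, and report it.
5. Describe the outcome as parent-reported with an unblinded respondent.

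The cost is IRB and consent wording to share contact details between sites (access to the roster is now restricted), some scheduling effort, and the loss of a coordinator whom the family knows. The last point matters because the plan leans on coordinator contact for its target of more than 85% follow-up. The local coordinator can keep the reminders and booking and hand over only the interview.

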Continued Anticonvulsants After Resolution of Neonatal Seizures: A Patient-Centered Comparative Effectiveness Study Last IRB approval: 04/20/2020 NCT02789176

RESEARCH STRATEGY

A. Background

Seizures affect ~16,000 newborns/year in the United States and have lasting adverse impacts on affected children and their families. About 15% of newborns with seizures die, and at least 50% of survivors have one or more long-term disability, including cerebral palsy, intellectual disability, and/or epilepsy¹. Many survivors require costly lifelong therapies, as well as social and academic support. More than 20% develop epilepsy within the first 12-18 months of life, and those with comorbid cerebral palsy are at highest risk^{2,3}. For the 1 in 26 Americans who have epilepsy, a history of neonatal seizures is a major risk factor for non-remittance (lack of complete response to medications)⁴. As such, neonatal seizures have a major impact, not only on the health of newborn infants, but also on their long-term neurological morbidity and chronic epilepsy [Criterion 1]. Despite the wide-ranging impacts of seizures in the newborn, alarmingly significant knowledge gaps persist [RQ-1]. The current management paradigm for neonatal seizures is to treat clinical events, with or without confirmation of EEG seizures, which can lead to both under- and over-treatment. Phenobarbital, the most commonly prescribed anticonvulsant, is often maintained for several months because of clinicians' and parents' concern that early discontinuation of medicine might cause seizures to recur⁵. However, continued exposure to phenobarbital is sedating, which may prolong the time it takes for a newborn to establish oral feeding, and this medicine may have deleterious long-term effects on the developing brain^{6,7}. Preliminary evidence suggests that early discontinuation of medication is not harmful, ^{5,6,8} but the optimal duration of therapy remains unknown. Parents of infants with neonatal seizures, including those involved in this proposal, highlight the lack of

certainty regarding treatment duration as a major concern.

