Neonatal seizures that are due to brain injury (acute symptomatic seizures) are difficult to treat, harm the developing brain, and are associated with long-term neurodevelopmental disabilities, including intellectual disabilities, autism, epilepsy, and cerebral palsy¹. Although acute symptomatic seizures are self-limited in the neonatal period, ≥20% of patients will go on to develop epilepsy (the neonatal seizures resolve, but the infant develops recurrent, unprovoked seizures later in life) and the highest risk is in the first year of life. Recommendations for immediate treatment of neonatal seizures are based largely on pre-clinical studies which show that seizures are injurious to the developing brain through alterations in neurogenesis, neuronal loss, and excitability¹³⁻¹⁶. However, traditional and commonly used anticonvulsant medications, such as phenobarbital, are potentially neurotoxic¹⁷ and are associated with lower cognitive scores when used long-term^{6,7}. Despite this, phenobarbital, the most commonly prescribed first line medication¹⁸, is often administered for up to several months, even without electrographic confirmation of seizures⁵. A randomized, controlled trial to examine the risks and benefits of continued treatment with phenobarbital following resolution of acute symptomatic seizures (PROPHENO - NCT01089504) failed due to lack of enrollment. The fundamental management question of how long to treat seizures in the neonatal period remains unanswered. Thus, a large-scale observational study is urgently needed, to inform the critical decision regarding duration of treatment for acute symptomatic neonatal seizures¹⁹.

Our long-term goal is to improve neurodevelopmental outcomes following acute symptomatic seizures in newborns. The objective of this application is to examine whether the duration of treatment with phenobarbital has an impact on neurodevelopmental and epilepsy outcomes, as well as parent and family wellbeing, after neonatal seizures. Our collaborative research team has established the *Neonatal Seizure Registry* - a multi-center association of institutions across the United States - and has partnered with Parent Partners and

NICU Patient & Parent Advocacy groups to develop the patient centered questions and outcomes outlined in this application.

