We have chosen functional developmental outcome as a primary outcome measure because our Parent Partners, stakeholders, and survey respondents have *all* told us that neurodevelopment and milestones are what matter most to parents in the first year of life: *"If the patient is taking medications, the parent will want to know about the risk and how those risks can impact milestones... We are all consumed, almost to the point of obsessed, with milestones early on. Each one that we don't make is another heart break."* Furthermore, parents value outcome measures that are simple and can be rapidly administered.

We hypothesize no difference in developmental milestones, as measured by the WIDEA FS, between infants who were prescribed short *versus* prolonged duration of phenobarbital. As discussed below, the study is powered as a *non-inferiority analysis* to detect a clinically relevant difference (<7%) on the WIDEA FS. This difference is both clinically meaningful and relevant to parents and stakeholders: in the county of San Francisco, which includes one of the study centers, patients must be at least 33% delayed prior to age 24 months to merit referral for developmental services²⁶ (e.g. functioning at the level of a 12-month-old when the child is 18-months of age). Therefore a difference of, at most, 7% would fall well below a clinically relevant threshold.

Secondary outcomes.

a) Epilepsy (Aim 1b) is one of the most dreaded complications after neonatal seizures. The seizures of newborns with acute symptomatic seizures resolve, but up to 20% will later develop recurrent unprovoked seizures (epilepsy). This pattern is distinct from newborns whose seizures are caused by neonatal-onset epilepsy (those infants are excluded from this study). A history of seizures in the newborn is a major risk factor for non-remittance of post-neonatal epilepsy⁴ and many affected children have very difficult-to-treat epilepsy, such as infantile spasms²⁷. Parent survey respondents indicated major concerns about the risk of epilepsy. If prolonged treatment of acute symptomatic neonatal seizures was shown to decrease the risk of epilepsy, then subtle associated cognitive consequences of the medication might be acceptable to parents, according to our Parent Partners. The members of the University of Michigan Patient and Family Research Council also highlighted the development of early, accurate predictors of unfavorable outcomes as priorities for research.

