Aim 1a: Our hypothesis is that short duration treatment with phenobarbital will be inferior to long duration by no more than a non-inferiority margin of 7% in our primary outcome (functional developmental outcome, measured by the WIDEA FS) adjusted for propensity for maintenance of phenobarbital. This margin is well below the clinically-significant threshold since a developmental delay of more than 33% is needed before a child may access developmental services 26. If there is truly no difference in neurodevelopmental outcome among children who had short versus prolonged treatment with phenobarbital (Aim 1a), and using a 12 month WIDEA FS mean of 109 with standard deviation of 16.5 (Appendix 3), we calculate that 192 subjects are required to be 80% sure that the lower limit of a one-sided 95% confidence interval will be above the noninferiority limit of -7. The WIDEA (our primary outcome measure) is also validated for age 24-months. At age 24-months, the standard deviation of the WIDEA is lower than at 12 months, which will improve our power to detect differences between the groups and, using a similar sample size, lower our non-inferiority margin from 7% to 4.25% for the primary outcome while also increasing accountability for loss to follow-up from 15 to 20%. . Therefore our proposed N=300 newborns, divided into N1 (short duration: phenobarbital discontinued prior to discharge) = 90, and N2 (prolonged duration: phenobarbital continued at discharge) = 210, allows us to take into account loss to follow-up (conservatively estimated at 15%) and propensity score adjustment analysis to address causal inference (as discussed below), which requires that we inflate the sample size by 9%²⁸. Aim 1b: We hypothesize that there is no clinically significant difference in epilepsy frequency between the groups. If there is truly no difference between short versus prolonged treatment, with epilepsy incidence conservatively estimated at 20%²⁷, then we will have sufficient subjects to be 80% sure that the upper limit of a one-sided 95% confidence interval (or equivalently a 90% two-sided confidence interval) will exclude a difference of more than 13% between groups²⁹. The clinical importance of a potential difference of 13% in epilepsy incidence between the groups depends, according to our stakeholders and parent partners, on the results of the primary neurodevelopmental outcome analysis. If developmental outcomes are not different between the short- and prolonged- treatment groups, then a difference of 13% in epilepsy incidence is meaningful and parents would be willing to accept prolonged medication treatment in hopes of reducing the risk for epilepsy. If developmental outcomes are disparate between the two groups, then parents say that the epilepsy risk is less important and they would prefer the treatment regimen that is least likely to produce developmental disabilities.

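### Aim 1b calls a 20% epilepsy rate conservative, but with an absolute 13-point margin only a high rate is conservative, and the documents disagree on whether 20% is high or low

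*Combined protocol and SAP*

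**What the plan says.** The Aim 1b paragraph of Sample Size Calculations assumes that the two groups have the same true rate, and works "with epilepsy incidence conservatively estimated at 20" percent. Its result is stated as 80% assurance, judged by a one-sided 95% bound, that the study "will exclude a difference of more than 13% between groups". The same section sets N = 300 as 90 short and 210 prolonged, allows 15% loss to follow-up (it also mentions 20%), and adds 9% inflation for propensity adjustment.

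Other sections describe the epilepsy rate differently:

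- A. Background: "More than 20% develop epilepsy within the first 12-18 months of life".
- Specific Aims, on acute symptomatic seizures: "≥20% of patients will go on to develop epilepsy".
- Outcome selection, secondary outcome (a): "up to 20% will later develop recurrent unprovoked seizures".
- Table 2 (pilot): epilepsy in 6 of 30 infants discharged on phenobarbital and 0 of 9 discharged off it.

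Aim 1 reads epilepsy at 24 months.

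**The concern.** The 13-point margin is a difference in absolute risk. The variance of a risk difference depends on p(1-p), which grows until p reaches 50%. A cautious planning rate is therefore an upper value for this population.

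Two sections present 20% as a lower value, and one of them places it before the 24-month reading. Cumulative incidence cannot fall with longer follow-up. A third section presents 20% as an upper value. The sample-size text uses the word that only the third section would justify.

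The plan gives the 13-point figure practical weight. Sample Size Calculations reports that, if development does not differ between groups, parents would regard a 13-point difference in epilepsy as meaningful and would accept prolonged medication. No developmental difference is the study's own hypothesis. If the excludable difference is larger than 13 points, the study could fail to rule out a difference that its stakeholders care about, while readers are told that the input was cautious.

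**Working it through.** **Inputs.** Margin 0.13 (read as absolute), true difference 0, one-sided alpha 0.05 (z = 1.645), 80% power (z = 0.842), 90:210 split, 15% loss and 9% inflation, all from Sample Size Calculations. The rates of 15%, 25% and 30% are sensitivity values. The 15% is close to the pooled pilot rate of 6/39 = 15.4%. The documents give no figure above 20%.

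**Formulas.**

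- SE = sqrt[p(1-p)(1/n1 + 1/n2)]
- Power = Φ(0.13/SE − 1.645)
- Difference excludable with 80% assurance = (1.645 + 0.842) × SE

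**Reproducing the stated figure at p = 20%.**

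- All 300 analysed (90/210): SE = sqrt[0.16 × (1/90 + 1/210)] = 0.0504. Power = Φ(2.579 − 1.645) = 82.5%; excludable difference 12.5 points.
- After 15% loss (76.5/178.5): SE = 0.0547; power 76.8%; 13.6 points.
- After 15% loss and division by 1.09 (70.2/163.8): SE = 0.0571; power 73.7%; 14.2 points.
- Equal groups of 117 (300 × 0.85 / 1.09 = 234 in total): SE = 0.0523; power 80.0%; 13.0 points.

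Of the variants tried, only equal groups return 80% and 13 points, and equal groups are not the planned split. With no loss and no inflation, 90:210 meets at least 80%. Once the stated loss is taken, it does not, even at 20%.

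**Sensitivity to the rate at 90:210.** Each cell gives power at 13 points, then the difference excludable with 80% assurance.

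| Rate | All 300 | After 15% loss | After 15% loss and 9% inflation |
|---|---|---|---|
| 15% | 89%; 11.2 | 85%; 12.1 | 82%; 12.7 |
| 20% | 82.5%; 12.5 | 77%; 13.6 | 74%; 14.2 |
| 25% | 77%; 13.6 | 71%; 14.7 | 68%; 15.4 |
| 30% | 73%; 14.4 | 67%; 15.6 | 63%; 16.3 |

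Moving from 20% to 25% costs about 6 points of power and adds 1.0 to 1.2 points to the excludable difference. Moving down to 15% gains about 7 to 8 points of power. The highest rate that keeps 80% power at 13 points is about 22% with all 300 analysed, 18% after loss, and 16% after loss and inflation.

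**Is 20% high or low?** The Background (above 20% by 12-18 months) and the Specific Aims (20% or more, no time horizon) make it a lower value. The outcome section makes it an upper value. The pooled pilot rate of 15.4% lies below it, but the exact 95% interval is about 6% to 31%. Follow-up in the pilot began at 6 months, and only 31 of the 39 infants were seen at 12-18 months or later.

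**The case against.** The strongest defence is that 20% may well be a high value. The section that defines the Aim 1b outcome treats it as a ceiling. The pilot infants are described as meeting the enrolment criteria, and their pooled rate is lower. The Background sentence concerns newborns with seizures in general, whereas the study excludes neonatal-onset epilepsy, malformations and genetic syndromes. The Specific Aims figure includes exactly 20%. The source cited for the planning rate cannot be consulted here.

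Much of this stands. A reader might infer that 20% is an optimistic input, or that 25-30% should be the planning rate. The documents support neither. Nor do they support saying that 13 points is out of reach under any split or loss rate: 90:210 without loss keeps 80% power up to about 22%, and 150:150 without loss gives SE = sqrt(0.1875 × 2/150) = 0.050 and 83% power even at 25%, although that is not the planned split.

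The 15% loss may also be too high for this outcome. Appendix 6 expects medical record review to reveal an epilepsy diagnosis when a family cannot be reached. The true position may then lie between the first two columns of the table.

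The defence does not rescue the label. The Specific Aims sentence concerns acute symptomatic seizures, the study's own population, so the documents give a floor and a ceiling for the same infants. The pilot is too small and too short to decide between them.

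**Conclusion.** The statement is wrong as written, in a limited sense. The label is unsupported and is contradicted by the Background and the Specific Aims, but 20% is not shown to be too low. What is established is a contradiction about an input to which the stated power is sensitive: from 15% to 30%, the excludable difference at 90:210 runs from 11.2 to 14.4 points with everyone analysed, from 12.1 to 15.6 after 15% loss, and from 12.7 to 16.3 after loss and inflation.

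Separately from the rate, the stated 80% at 13 points is not delivered by the planned split after the plan's own 15% loss, even at 20% (76.8%, or 73.7% with the inflation). Correcting the wording about the rate would not cure that.

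These results assume an absolute margin, equal true rates, the normal approximation, and loss in equal proportion in both groups. Rates above 20% are assumptions. Epilepsy is a secondary outcome, so the primary sample size is not affected.

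**What to change.** Reconcile the epilepsy rates in the Background, the Specific Aims, the secondary-outcome text and Sample Size Calculations, giving for each the population and the age to which it applies. Remove the claim that 20% is conservative.

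Replace the single 80%/13-point statement with the difference excludable with 80% assurance at the 90:210 split over an assumed range of 15-30%, as in the table, with rates above 20% labelled as assumptions. State the loss assumed for epilepsy and whether record review is expected to bring it below 15%.

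The cost is a rewritten paragraph and a less favourable figure. No extra patients and no change of analysis are needed.
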